### **Side Effects Related to Study Drug**

#### ***Common Side Effects***

- Hyperkalemia: We anticipate that approximately 1% of patients may develop serious hyperkalemia that may warrant discontinuation. However this may be considerably higher in patients with GFR of 40-50 ml/minute who will constitute a minority of the patients in the trial.
- Increases in BUN and creatinine
- Gynecomastia or breast discomfort. Gynecomastia is a well-described adverse effect of spironolactone and is related to dose and duration of treatment; we anticipate that

approximately 10% of patients may develop gynecomastia that may warrant discontinuation. Generally, discontinuation of treatment results in resolution of gynecomastia.

### **Other Side Effects**

- Cardiovascular: Vasculitis
- Central nervous system: Ataxia, confusion, drowsiness, headache, lethargy
- Dermatologic: Erythematous maculopapular rash, Stevens-Johnson syndrome, toxic epidermal necrolysis, urticaria
- Endocrine & metabolic: Amenorrhea
- Gastrointestinal: Abdominal cramps, diarrhea, gastritis, gastrointestinal hemorrhage, gastrointestinal ulcer, nausea, vomiting
- Genitourinary: Impotence, irregular menses, postmenopausal bleeding
- Hematologic & oncologic: Agranulocytosis, malignant neoplasm of breast
- Hepatic: Hepatotoxicity
- Hypersensitivity: Anaphylaxis
- Immunologic: DRESS syndrome
- Renal: Increased BUN, renal failure, renal insufficiency
- Miscellaneous: Fever

### **Potential Benefits of the Proposed Research to the Subjects and Others**

It is possible that there may be a benefit with Spironolactone in terms of organ protection and patients may see benefits relating to reduction of atherosclerotic plaque including reduction in risk for events such as heart attacks, stroke, renal failure and need for hospitalization. The potential benefits must obviously be contrasted with the risk for renal failure and hyperkalemia.

### **Importance of the Knowledge to be Gained**

There is an urgent need for clinical trials aimed at reducing the disproportionate cardiovascular disease burden and mortality in Type II diabetes. The multiple cardiovascular benefits of mineralocorticoid receptor (MR) blockade (using spironolactone or eplerenone) are well recognized in patients without Type II diabetes in the setting of congestive heart failure or myocardial infarction. However, randomized trials of MR Blockade have not been conducted in patients with atherosclerosis. A potential role for MR blockade for slowing atherosclerosis progression as well as influencing cardiovascular outcomes in diabetic patients is only beginning to attract the attention of cardiologists. Patients with atherosclerosis may benefit from MR blockade if, on one end of the spectrum, such intervention is made relatively early in the course of Type II diabetes to slow progression and of atherosclerosis and inflammation or plausibly at the other extreme when patients are already at very high risk patient population for cardiovascular events and mortality. The use of Spironolactone in patients with type II diabetes and atherosclerosis has not been well studied.

### **STUDY OBJECTIVES**

#### **Primary Objective**

Evaluate the impact of Spironolactone in reducing atherosclerosis plaque as measured by change in percent total atheroma volume (PAV) in thoracic aorta with Spironolactone vs. placebo.

[figure not shown]
## Secondary Objectives

Evaluate the functional significance of candidate miRNAs. Compare monocyte polarization and inflammatory gene expression at 6-weeks. Evaluate miRs expression to predict atherosclerosis and response.

## STUDY DESIGN

### Vanguard Phase

[figure not shown]
Prior to the Main Study Phase, an open label vanguard (pilot) phase is planned with 10 subjects over 4 weeks with Spironolactone. This phase is designed to provide preliminary evidence and assess recruitment and methods.

**Figure 7. Vanguard Phase**

### Main Study Phase

The Main Study Phase is a multi-site, double-blind, randomized, placebo-controlled trial with spironolactone. 130 subjects are planned. There will be 4 phases (screening, placebo run-in, dose escalation and treatment phase (FIG. 8). All patients will be carefully evaluated for study eligibility during screening prior to randomization and will be recruited from clinics at the University Hospitals Cleveland Medical Center as well as nephrology clinics. The 2-week single-blind lead-in period will permit assessment of patient compliance as well as determination of baseline sitting blood pressures. Patients must have met all inclusion/exclusion criteria before being randomized 1:1 to Placebo or Spironolactone 12.5 mg on Week 0 (Visit 2). Patients will be escalated to 25 mg daily Spironolactone or maximal tolerated dose over a 4-week period with safety checks on K+ and creatinine (FIG. 8).

## CRITERIA FOR EVALUATION

### Co-Primary Efficacy Endpoints

The co-primary outcome measure is change in 24-hour SBP in Spironolactone treated patients versus placebo and percent change in total atheroma volume (PAV) in thoracic aorta of Spironolactone vs placebo.

### Secondary Efficacy Endpoints

Change in central aortic SBP, Change in central aortic DBP, Change in central aortic Mean BP, 24-hour mean ambulatory BP, 24-hour ambulatory diastolic blood pressure, and HOMA-IR.

Evaluate miRs involved in regulating MR expression and differentially regulated miRs as predictors of disease progression and response.

Compare monocyte inflammatory activation in Spironolactone vs placebo at 6-weeks.

Investigate pre-miR/mimics and antagonomirs to regulate NR3C2 expression and alternate macrophage phenotype in human macrophages.

### Safety Evaluations

Change in clinical laboratory findings (e.g. BUN, Creatinine, electrolytes).

Incidence of adverse events

## SUBJECT SELECTION

### Study Population

Subjects with a diagnosis of Type II Diabetes who meet the inclusion and exclusion criteria will be eligible for participation in this study. Labs drawn within 3 months of the screening visit may be used to determine eligibility.

### Inclusion Criteria

1. Male or female patients > 45 or > 40 years with known atherosclerotic events (examples include MI, Stroke) and able to provide informed consent (females must be either post-menopausal for one year, surgically sterile, or using effective contraception. Oral contraceptives are disallowed).
2. Patients with type II diabetes with HbA1c ≤ 9.0 on stable anti-glycemic regimen that may include oral and/or injectable therapy (GLP-1/Insulin etc.). Changes in dose of glycemic regimen is allowed during the course of the trial if felt to be clinically appropriate.

3. GFR <90 and evidence of proteinuria (Urine Albumin/Creatinine Ratio of >30 mg/g or equivalent) in a urine specimen within 12 months OR GFR <60 mg/g regardless of proteinuria.
4. Patients must be on ACE and/or ARB therapy with no planned dose adjustments.

#### **Exclusion Criteria**

1. Uncontrolled hypertension (SBP>160 and/or DBP>95 mmHg at visit 0 (screening) Protocol Number: 09-16-32 Confidential Version #: 1.5 Revised 01 April 2020 Page 14 of 39 and SBP >145 mm Hg at visit 2).
2. GFR (MDRD) of <15 at visit 0 (screening)
3. Hyperkalemia defined as serum K+ $\geq$  5.1 meq/L at visit 0 (screening)
4. LDL cholesterol >150 mg/dL
5. Plasma triglycerides > 400 mg/dl
6. Contraindications to MRI (metallic implants, severe claustrophobia).
7. Acute coronary syndrome, Transient ischemic attack, CVA or critical limb ischemia during the last 6 months or coronary/peripheral revascularization within the last 3 months.
8. Evidence of a secondary form of hypertension
9. Initiation of new therapy with statins, ACEI/ARB, antioxidants, CCBs, diuretics,  $\beta$  blockers
10. Type I diabetes mellitus
11. Known contraindication, including history of allergy to Spironolactone
12. Any surgical or medical condition which might alter pharmacokinetics of drug (e.g. renal transplant, liver failure, liver transplant)
13. Concurrent potentially life threatening arrhythmia or symptomatic arrhythmia.
14. Significant hyponatremia defined as Na<130 meq/L
15. History of prior malignancy including leukemia and lymphoma (but not basal cell skin cancer, cured squamous cell cancer and cured prostate cancer).
16. History of any severe, life-threatening disease.
17. Any surgical or medical conditions which place the patient at higher risk derived from his/her participation into the study, or likely to prevent patient from complying with requirements
18. History of drug abuse within the last 2 years, noncompliance and unwillingness/inability to consent
19. Pregnant women and nursing mothers
20. Class III or IV Congestive Heart Failure
21. Primary Hyperaldosteronism

#### **Recruitment Strategy**

All patients will be carefully evaluated for study eligibility during screening prior to randomization and will be recruited from clinics at University Hospitals' healthcare systems. The medical records will be accessed to determine eligibility. PHI will be accessed during the pre-screening portion for medical review. A full waiver is requested. The 2 -week single -blind lead--in period will permit assessment of patient compliance as well as determination of baseline sitting blood pressures. Patients must have met all inclusion/exclusion criteria before being randomized 1:1 to Placebo or spironolactone on Week 0 (Visit 2). We may call patients who have expressed interest in the stud, using an approved phone script. No cold calling will be done. The phone script will be used for patients who would like to be contacted

regarding more information about the study after their physician has given them some initial background in person or by letter.

## **CONCURRENT MEDICATIONS**

All subjects should be maintained on the same medications throughout the entire study period, as medically feasible. Changes in dose of glycemic regimen is allowed during the course of the trial if felt to be clinically appropriate. Patients must be on ACE and/or ARB therapy and statin therapy with no planned dose adjustments.

## **Prohibited Medications and Treatments**

The following medications are prohibited during the study:

Oral contraceptives

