## BACKGROUND

Pharmacological studies over > 20 years have defined the importance of the mineralocorticoid receptor (MR) in hypertension and heart failure. Large-scale clinical trials have validated the use of MR antagonists in the management of patients with heart failure (RALES, EMPHASIS) and post myocardial infarction (EPHESUS)1-4 . Recent studies suggest that MR may link metabolic dysregulation with susceptibility to type II diabetes (T2DM) and atherosclerosis5-12 . MR is an ancient member of the 51-member, steroid-thyroid-retinoid receptor family. In response to ligand binding, MR undergoes conformational changes and is translocated to the nucleus where it binds to response elements in promoters, increasing transcription of target genes 13,14 . Although effects of MR activation have been attributed to aldosterone, mechanisms independent of aldosterone have been suggested and play a role in promoting inflammation, fibrosis and target organ damage15-18 .

**Cardiovascular Effects of MR Activation:** MR is widely expressed in the cardiovascular system 19-22 and is a major determinant of endothelial function, smooth muscle tone, vascular remodeling, fibrosis and blood pressure (BP)23-36 . In vitro, animal, and human data support a role for MR activation in promoting vascular oxidative stress, inflammation, proliferation, migration, vasoconstriction, vascular remodeling and fibrosis (FIG. 2) 5,28,31,36-44 . Similarly, MR antagonism is anti-inflammatory and antifibrotic with evidence in humans indicating reversal of endothelial dysfunction, diastolic dysfunction and vascular stiffness45-49 .

[figure not shown]
**FIGURE 2.** Adverse consequences of MR activation.

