**Assessment of Aortic Atherosclerosis at 3.0T MR using SPACE:** We have described the implementation of a modified spin echo sequence T1W-SPACE and have successfully implemented this technique at both 1.5T and 3.0T. We have developed a customized tool-set for assessment of plaque area over the aorta.

**Plaque Progression over 9 months:** In a recently concluded study in patients with established vascular disease on complete renin blockade with Aliskiren (ALPINE, n=37). The results of this study demonstrated that aliskerin use on top of ACEI/ARB progresses atherosclerosis. These results are consistent with results of ALTITUDE published recently. Interestingly one of the findings in the study was that aliskerin treatment resulted in decrease of miR-19a which we have shown to be important in upregulation of MR. This increase was particularly robust in those on ACEI/ARB therapy suggesting that this group could be potentially sensitive to the effects of MR blockade as they are overexpressing MR (product of NR3C2 gene).

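### No eligibility criterion or prohibited-drug entry covers patients already taking a mineralocorticoid receptor antagonist, so they can be randomised and weaken the contrast under test

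*Combined protocol and SAP*

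**What the plan says.** - **Prohibited Medications and Treatments:** the section opens "The following medications are prohibited during the study" and lists oral contraceptives, with no other entry.
- **Concurrent Medications:** "All subjects should be maintained on the same medications throughout the entire study period, as medically feasible". No washout of any drug is described.
- **Inclusion and Exclusion Criteria:** none of the 4 inclusion or 21 exclusion criteria mentions current use of an MR antagonist. The nearest are exclusion 9, "Initiation of new therapy with statins, ACEI/ARB, antioxidants, CCBs, diuretics" (the list ends with beta blockers), and exclusion 11, "Known contraindication, including history of allergy to Spironolactone".
- **Heart failure and MI:** exclusion 20 removes "Class III or IV Congestive Heart Failure", which leaves classes I and II eligible. Inclusion 1 gives MI as an example of a qualifying event, and exclusion 7 removes acute coronary syndrome only within the last 6 months.
- **Background:** "Large-scale clinical trials have validated the use of MR antagonists in the management of patients with heart failure (RALES, EMPHASIS) and post myocardial infarction".
- **Formulation of Test Product:** spironolactone is described as both a potassium-sparing diuretic and an MR antagonist.

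**The concern.** The primary objective needs a group receiving MR blockade and a group not receiving it. A placebo patient already taking an MR antagonist does not supply the second condition. A user assigned to spironolactone either takes more of the same drug or adds it to another member of the class, so the added effect may be smaller than the design assumes. Both mechanisms pull the treatment difference toward zero for the two co-primary endpoints (PAV and 24-hour systolic pressure) and for the monocyte outcomes.

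The possibility is not remote on the protocol's own account. The Background names two settings in which the class is validated, and part of each remains eligible.

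There is also a safety side. ACE inhibitor or ARB therapy is required, a GFR as low as 15 is admitted, and the Hyperkalemia Management section says this population is already at raised risk. Duplicated or added MR blockade would occur on top of that. The anticipated rate of about 1% serious hyperkalemia, given under Side Effects Related to Study Drug, is not stated with such patients in view.

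**Working it through.** **Step 1. Can an established user get through the criteria as written?** Take a patient on a stable MR antagonist, with an MI two years ago and normal potassium.

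| Provision | Does it stop this patient? |
|---|---|
| Exclusion 3 (potassium of 5.1 or above at screening) | No; potassium is normal |
| Exclusion 7 (recent acute events) | No; the event is older than 6 months |
| Exclusion 9 (initiation of new therapy) | No; therapy is established |
| Exclusion 11 (contraindication or allergy) | Not clearly; current use is not named |
| Exclusion 17 (higher-risk conditions) | At the investigator's discretion; it concerns conditions, not drugs |
| Exclusion 20 (class III-IV heart failure) | No |
| Counselling under Hyperkalemia Management | Advice only; the examples are NSAIDs and salt substitutes |
| Prohibited list | No; oral contraceptives only |

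Once enrolled, the patient falls under the instruction to remain on existing drugs. No provision is a firm bar.

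**Step 2. Reproduce the plan's sample size.** Inputs from Aim 1 of the Statistical Methods: CV 0.83, 1.5-fold difference, alpha 0.05, 80% power, 20% loss. The general considerations supply two-sided tests and log transformation.

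- Log-scale SD = sqrt(ln(1 + 0.83²)) = 0.724
- Log effect = ln(1.5) = 0.405; standardised effect = 0.405 / 0.724 = 0.560
- Two-sample t test: 52 per group (normal approximation: 51)
- Total = 104 / (1 − 0.20) = 130

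Both stated figures reproduce, and the t test matches all nine cells of Table 7. Exact power at 52 per group is 80.8%.

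**Step 3. Illustrate the dilution.** Assume that a share f of each arm already takes an MR antagonist and gains nothing from assignment, with the SD unchanged. The documents do not give f. The average log effect becomes ln(1.5) × (1 − f).

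| f | Diluted fold difference | Power at 52 per group | n per group for 80% | Total with 20% loss |
|---|---|---|---|---|
| 0 | 1.50 | 80.8% | 52 | 130 |
| 5% | 1.47 | 76.7% | 57 | 143 |
| 10% | 1.44 | 72.1% | 63 | 158 |
| 20% | 1.38 | 61.9% | 80 | 200 |

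Totals are 2n / 0.80, rounded up. The calculation covers PAV only, because the Statistical Methods give no sample-size figures for 24-hour systolic pressure.

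**The case against.** The strongest reply is that the protocol is not silent on every route. Exclusion 11 does not itemise contraindications, so a site might count current use as one. Exclusion 17 gives the investigator discretion. The hyperkalemia counselling is worded broadly, and its named items are only examples. In practice, sites may turn such patients away. This stands as a reason to expect f to be small. It does not close the gap, because none of these is a rule on MR antagonist use and sites could apply them differently.

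The magnitude also depends wholly on assumptions. With f near zero nothing changes; at 5% power is still about 77%. Zero added effect is the pessimistic case, since a user given more MR blockade might still respond. That stands too.

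Some stronger readings are tempting, but the documents do not support them:

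- *The protocol allows open-label MR antagonists to be started during the trial.* The short prohibited list might suggest this. However, the Concurrent Medications section asks for unchanged medication as far as feasible, which discourages new starts. The gap concerns established use.
- *No analysis could address the problem.* The Aim 1 analysis plan allows further confounders and clinically relevant interactions, the medication log records the drugs, and a detailed SAP is still to be written. Such an analysis is feasible, although its power would be low and none is named at present. Covariate adjustment alone would not create a contrast that such patients never had.
- *Aliskiren belongs in the same argument.* Preliminary Studies reports that "aliskerin use on top of ACEI/ARB progresses atherosclerosis", but aliskiren is not an MR antagonist. The same paragraph suggests that the patients concerned could be more sensitive to MR blockade, which does not imply bias toward no difference.
- *Every user in the active arm receives a second MR antagonist.* An existing spironolactone user would receive more of the same drug.

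**Conclusion.** The omission is real and is established from the text alone: as written, the plan can randomise patients who already take an MR antagonist. The direction of the effect is dilution toward no difference in PAV, 24-hour systolic pressure and the monocyte outcomes, with duplicated or added MR blockade in the active arm as a separate safety matter.

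The size is unknown. Power of 77%, 72% or 62% at f = 5%, 10% or 20% is an illustration under three assumptions: equal prevalence in the arms, no added effect in users, and an unchanged log SD. A reader might take these figures as a forecast of lost power, but the documents give no prevalence to support that. The case for acting rests on protecting the tested contrast and on safety, at low cost.

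**What to change.** **Patients not yet randomised.** Add to the Exclusion Criteria a criterion on current use of a non-study MR antagonist (spironolactone, eplerenone or another of the class), with the lookback window set by the sponsor's clinical team. Reconcile Concurrent Medications and Prohibited Medications and Treatments with it, so that the instruction to keep existing drugs no longer conflicts with eligibility. The COVID-19 section describes patients held in run-in before Visit 2; they can be checked against the new criterion before randomisation.

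**Patients already randomised.** The amendment cannot reach them. Use the medication log, which Table 4 schedules from screening onward, to identify baseline and on-study MR antagonist use, and report both by arm. Pre-specify in the SAP a sensitivity analysis of both co-primary endpoints by that use. Baseline use precedes randomisation, so comparing arms among non-users at baseline remains a randomised comparison. On-study use arises after randomisation, so analyses by it need more cautious interpretation.

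**Left to the sponsor.** The handling of study drug if an MR antagonist becomes clinically necessary is a clinical decision for the sponsor to state.

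**Cost.** One added criterion, two reconciled sections and one SAP paragraph. No new data collection is needed. Expect a few more screen failures among post-MI and mild heart failure patients, and a mid-trial change in the eligible population that the report should describe.

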## **STUDY TREATMENTS**

### **Method of Assigning Subjects to Treatment Groups**

After the placebo run-in phase, eligibility with regards to blood pressure will be reassessed.

Up to 130 eligible patients will be randomly assigned to Spironolactone or placebo treatment groups in a 1:1 ratio using a computer-generated randomization scheme developed by the statistician.

All study participants will undergo a two week run-in period with placebo. Then study medication will be commenced at 12.5 mg Spironolactone or placebo and escalated to 25 mg Spironolactone or placebo over 4 weeks. Then the treatment phase will commence with tolerated dose of Spironolactone or placebo for 48 weeks.

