#### **Treatment of hyperkalemia for Potassium > 6.0 meq/L**

If the potassium level is > 6.0 mEq/L, the study medication will be held until the level decreases to < 5.5 mEq/L.

Acutely to treat the potassium:

An ECG should be checked. If there are no ECG changes and potassium level is < 6.5, then Kayexalate alone (60 grams) may be sufficient. If there are ECG changes, treatment would include insulin/glucose, beta-agonists and possibly calcium and bicarbonate. If there are ECG changes or if the potassium level is > 6.5 meq/L, the patient should be treated in the emergency room. If there are ECG changes, the patient should be placed on a cardiac monitor.

Reinstitution of Study Medication

If the potassium level was > 6.5, then the study medication will be permanently discontinued and the patient will be removed from the trial. If this is the second episode where potassium > 6.0, then the study medication will be permanently discontinued and the patient will be removed from the trial.

Recheck potassium level 7- 14 days after discontinuation. If K+ is > 5.5 mEq/L, do not restart study medications. Repeat potassium again in 7-14 days. If K+ is ≤ 5.5 mEq/L, the study medication will be reinstated at 50% of prior dose.

If the study medication was restarted, check potassium level again in two weeks, if K+ is:

- o > 6.0: stop study the study medication permanently
- o 5.5-6.0: treat K+, maintain current dose of the study medication
- o < 5.5: mEq/L and patient is on at least 12.5 mg spironolactone, increase spironolactone to 25mg daily.

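### In the available text, the K+ entry limit applies only at screening; no K+ value on the Visit 2 BMP has to be met before spironolactone is started

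*Combined protocol and SAP*

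**What the plan says.** Under Exclusion Criteria, exclusion 3 removes patients with serum K+ at or above "5.1 meq/L at visit 0 (screening". Study Population adds: "Labs drawn within 3 months of the screening visit may be used to determine eligibility." Blood pressure is handled differently. Exclusion 1 has a screening limit and a second one, "and SBP >145 mm Hg at visit 2", and Method of Assigning Subjects to Treatment Groups states: "After the placebo run-in phase, eligibility with regards to blood pressure will be reassessed."

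Main Study Phase and Recruitment Strategy both require every criterion to be met before randomisation at Visit 2. Table 4 places a BMP in the Visit 2 (W4) column, with further BMPs at W5 and W6. Main Study Phase describes escalation from 12.5 mg with "safety checks on K+ and creatinine (FIG. 8"; that figure is not available.

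Hyperkalemia Management sets graded responses: a low-potassium diet above 5.0, conservative measures above 5.5, and a hold above 6.0: "If the potassium level is > 6.0 mEq/L, the study medication will be held until the level decreases to < 5.5 mEq/L." After a hold: "If K+ is > 5.5 mEq/L, do not restart study medications." For patients already restarted, the rule is "5.5-6.0: treat K+, maintain current dose of the study medication", and below 5.5 a patient on at least 12.5 mg goes up to 25 mg. Urgent Study Alerts calls for immediate investigator notification at K+ of 6.0 or more. The Blinding section says safety K+ values are blinded and managed by protocol.

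**The concern.** The plan treats K+ of 5.1 as too high to enter the trial but does not apply that limit to the sample drawn when drug is started. Every patient must be on an ACE inhibitor and/or ARB, GFR may be as low as 15, and Hyperkalemia Management itself says that diabetic patients with chronic kidney disease are at increased risk. A patient whose K+ has risen since the qualifying lab could receive a first dose at a level that would have kept him or her out at screening. The stake is patient safety at first dose. The randomised comparison is not touched, because the gap acts before assignment and equally in both arms.

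**Working it through.** The claim rests on the rules as written. The plan gives no figure to reproduce.

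**1. Does the requirement to meet all criteria close the gap?** No. Exclusion 3 is dated to visit 0, so a visit 0 value below 5.1 satisfies it whatever the Visit 2 BMP shows.

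**2. How old can the qualifying K+ be at Visit 2?** With the screening draw, W4 − W1 = 3 weeks. With the 3-month allowance used in full, about 13 + 3 = 16 weeks. A Visit 2 postponed under the COVID-19 plan adds to this.

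**3. What happens at each Visit 2 value,** if the follow-up rules are read to apply at that visit?

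| Visit 2 K+ (meq/L) | Same value at visit 0 | Response in the text | May drug start? |
|---|---|---|---|
| 5.1 to 5.5 | Excluded | Diet | Yes |
| Above 5.5 to 6.0 | Excluded | Diet, conservative measures; alert at exactly 6.0 | Yes |
| Above 6.0 | Excluded | Hold and ECG | No, if the hold covers a first dose |

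**4. How strong is the inconsistency in each band?** Above 5.5, the plan lets a new patient begin but would not let a held patient restart. The parallel is imperfect: the restart bar concerns patients who have already exceeded 6.0, and a restarted patient found at 5.5 to 6.0 two weeks later stays on drug. At 5.1 to 5.5 there is no conflict with the on-treatment rules, since the plan raises the dose below 5.5 in restarted patients. There the point is only that the entry limit is not applied when dosing begins.

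**5. What bounds the exposure?** The starting dose is 12.5 mg. The next BMP is at W5, 7 days after W4, or 5 to 9 days with the 2-day window on W5. Another follows at W6, and drug is held above 6.0. The repeat BMPs come after the first dose.

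**6. Can frequency be estimated?** No. The documents give no K+ distribution. To show how far an answer depends on what is assumed, let a patient's true level be T ~ N(m, s_b²) and each draw be T + e, with e ~ N(0, s_w²) and no drift. Then P(second draw in band | first < 5.1) = ∫P(first < 5.1 | t)·P(second in band | t)·f(t)dt ÷ ∫P(first < 5.1 | t)·f(t)dt. All inputs below are assumptions.

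| m, s_b, s_w | 5.1 to 5.5 | Above 5.5 to 6.0 | Second draw and a repeat both ≥ 5.1 |
|---|---|---|---|
| 4.3, 0.25, 0.20 | 0.5% | below 0.01% | 0.07% |
| 4.3, 0.35, 0.25 | 2.1% | 0.1% | 0.5% |
| 4.5, 0.35, 0.30 | 6.0% | 0.7% | 1.8% |
| 4.7, 0.35, 0.40 | 12.9% | 3.7% | 5.6% |

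With 130/2 = 65 patients on spironolactone, the band above 5.5 runs from essentially none to 65 × 0.037 = 2.4 patients. The last row also implies that 23% fail K+ at visit 0. A span this wide is a reason to claim no frequency.

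**The case against.** The strongest reply is that the plan is not silent on this range. It prescribes diet above 5.0, conservative measures above 5.5 and an alert at 6.0, and even up-titrates restarted patients below 5.5. A screening limit tighter than the on-treatment limit is an ordinary margin. In the middle row of the table, about 90% of second draws at or above 5.1 (0.0602 of 0.0673) fall in the 5.1 to 5.5 band, where the plan tolerates continued treatment. Hyperkalemia Management also notes that a high value can be transient. This stands, and it keeps the point minor. It does not supply a limit for starting drug: the diet rule is framed for follow-up, and none of these responses withholds a first dose at 6.0 or below.

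Second, FIG. 8 may carry a Visit 2 limit, and the COVID-19 plan delays Visit 2 until labs can be done. The first is possible, so the finding covers the available text only. The second implies that labs accompany the start of drug but gives no threshold.

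Third, investigators have discretion: exclusion 17 covers patients at higher risk, and Dosage allows adjustment for K+. Neither names a K+ value for starting, and if the blinding of safety K+ covers the Visit 2 BMP, the investigator may not see the result.

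A reader might infer that such patients have no protection, or that starting drug at 5.1 to 5.5 breaks the plan's own treatment rules. The graded responses and the up-titration rule contradict both readings.

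**Conclusion.** The point holds as a minor safety gap. On the available text, a patient with Visit 2 K+ of 5.1 to 6.0 can be randomised and start spironolactone 12.5 mg, although the same value at visit 0 would have excluded that patient. The case is strongest above 5.5 and up to 6.0. At 5.1 to 5.5 it is only that the sponsor's entry limit is not applied at the time of dosing. The conclusion assumes that exclusion 3 means what it says about visit 0 and that FIG. 8 adds no limit. Confidence is medium for the latter reason. A reader might also infer a threat to the trial's result or a sizeable number of patients at risk. The documents support neither: the arm comparison is unaffected, and no frequency can be derived from them.

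**What to change.** In Exclusion Criteria and in Method of Assigning Subjects to Treatment Groups, require the Visit 2 BMP, or one drawn between Visits 1 and 2, to show K+ below 5.1 before randomisation and first dose. Allow one repeat draw, so that a transient high does not exclude a patient. Apply the same rule to Visit 2s postponed under the COVID-19 plan. If FIG. 8 already carries such a limit, copy it into those two sections.

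In Blinding, state that this pre-randomisation K+ is an eligibility value released to the investigator. That does not threaten the blind, because no treatment has been assigned when it is read.

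The threshold and the 3-month allowance for initial screening can stay. The cost is protocol wording, a short wait for the result, some repeat draws and a few extra screen failures. The BMP is already scheduled. Under the assumed distributions above, of 130 patients reaching Visit 2, fewer than 1 to about 22 would need a repeat draw (the upper figure is 130 × 0.1681) and at most about 7 would fail both draws (130 × 0.0557). These counts are illustrative only.
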